depression severity (Radloff, 1977). Anxiety symptoms will also be assessed at all three assessment points using the GAD-7, a 7-item self-report questionnaire used to measure the severity of anxiety symptoms (Spitzer, Kroenke, Williams, & Löwe, 2006). In order to determine clinically significant and combined reduction in alcohol use and comorbid emotional problems, we will use a combined outcome of alcohol use on the AUDIT, and cut-offs from the GAD-7 and CES-D. We will also measure participants' quality of life using the World Health Organization Quality of Life assessment (WHOQOL-BREF). This is a 26-item self-report measure that assesses functionality in various life domains (The WHOQOL Group, 1998). A sum score will be used to assess overall quality of life at all assessments points (i.e., T0-T2). We will also collect information on participants' use of other substances using the National Institute on Drug Use (NIDA ASSIST; National Institute on Drug Abuse, 2009), and their executive functioning using the WebEx (Buchanan et al., 2010). This information will be collected to examine transfer effects to other substances, as well as to examine the potentially moderating effects of executive functioning. Finally, we will obtain a measure of participants' level of motivation in terms of importance, confidence, and readiness. Participants will complete all measures at each of the three time points, with the exception of the Demographics questionnaire and the AUDIT, which will only be completed at baseline.

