## Statistical Analysis Plan

**Power Analysis:** A recent meta-analysis showed that combined CBT/MI resulted in statistically significant reductions in alcohol use and depressive symptoms, with effect sizes being in the small range in both clinical and subclinical groups ( $g=.17-.27$ ). Data show relatively comparable effect sizes for online and in person interventions for alcohol misuse and depression. Therefore, a small effect size ( $g=.25$ ) is expected for group differences in alcohol use and emotional symptoms at posttreatment. Using G\*Power, the required sample size to detect a small effect size is  $N=398$  (with power rate set at .80 and  $\alpha = .05$ ).

**Statistical Plan:** Before hypothesis testing, we will run preliminary analyses (e.g., baseline differences, missing data analyses). We will also examine overall group differences in clinically meaningful variables (i.e., % below moderate cut-offs on the AUDIT, CES-D, and GAD-7 after treatment and at follow-up). Next, Generalized Estimating Equations (GEE) will be used to evaluate the main hypotheses that integrated treatment will result in the largest reductions in alcohol use, depression, and anxiety. GEE is a multilevel modeling technique that is preferable to repeated-measures ANOVA for pre/post analyses, as it will allow us to include all randomized participants in analyses. This results in less bias due to missing follow-up data. However, due to potential attrition problems, we also plan to conduct a sensitivity analysis. Primary and secondary outcomes will be tested sequentially in a mixed within- (repeated assessments) and between-subjects (treatment condition) design.

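### The protocol's combined alcohol-and-mood outcome has no combination rule and no planned comparison in the SAP

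*SAP*

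**What the plan says.** Protocol, Method (Research Instruments): the stated aim is to determine "clinically significant and combined reduction in alcohol use and comorbid emotional problems", and for this "we will use a combined outcome of alcohol use on the AUDIT, and cut-offs from the GAD-7 and CES-D". This is a single outcome with a stated purpose. The section gives no AUDIT threshold, no numeric cut-offs for this outcome and no rule for joining the three parts. The same section has every measure completed at all three time points "with the exception of the Demographics questionnaire and the AUDIT, which will only be completed at baseline".

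SAP, Statistical Plan: among the steps listed before the GEE, the team will examine "overall group differences in clinically meaningful variables", given as the percentage "below moderate cut-offs on the AUDIT, CES-D, and GAD-7 after treatment and at follow-up". The GEE then addresses the hypotheses that "integrated treatment will result in the largest reductions in alcohol use, depression, and anxiety". No combined outcome appears anywhere in the SAP, and the moderate cut-offs are not given as numbers.

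Protocol, Participants: entry requires CES-D above 16 and/or GAD-7 above 5, so a participant can enter with one of the two mood scales below its entry cut-off.

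**The concern.** The trial's case for an integrated treatment is that drinking and mood feed each other, and that treating them separately may not be enough (Protocol, Summary of Project, Background). The combined outcome is the one measure in the protocol that would show whether individual participants improved on both.

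On its natural reading, the SAP reports the three scales side by side. A participant who falls below the CES-D cut-off and still drinks heavily raises one of those percentages, but has not achieved combined improvement. A treatment that moved only drinking, or only mood, could therefore look clinically meaningful on a single percentage while joint benefit went unexamined. If the combined outcome were wanted later, its thresholds and joining rule would still have to be chosen, possibly with the results in view.

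**Working it through.** **1. The two texts side by side.**

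| | Protocol, Research Instruments | SAP, Statistical Plan |
|---|---|---|
| Number of outcomes | one, combined | plural variables |
| Instruments | AUDIT, GAD-7, CES-D | AUDIT, CES-D, GAD-7 |
| Joining rule | not stated | not stated |
| Numeric cut-offs for this outcome | not stated | not stated |
| Planned comparison | none described | to be examined; no test, model or alpha |
| In the GEE hypotheses | – | no (alcohol use, depression, anxiety) |
| AUDIT after baseline | not collected | needed after treatment and at follow-up |

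The plural, and the one-by-one GEE hypotheses, favour separate percentages. On either reading the SAP has no rule and no test for the combined outcome.

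**2. The plan's own figure.** The only quantitative figure in the SAP's Power Analysis is N = 398 for g = .25, power .80, alpha .05. It reproduces as a one-sided two-sample t-test (199 per arm); a two-sided test gives 506. It concerns continuous differences and says nothing about responder rates, so it neither supports nor limits this point.

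**3. What three percentages say about joint success.** If a proportion p is below each of three cut-offs, the proportion below all three lies between max(0, 3p − 2) and p. For p = .50 this is max(0, −.50) = 0 to .50. For p = .40 it is 0 to .40. The separate percentages leave the joint rate almost undetermined.

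**4. Illustration.** The documents give no responder rates or correlations. Assumptions: 50% of controls below each cut-off; latent normal correlations of .2 (alcohol with each mood scale) and .6 (CES-D with GAD-7); success means below all three; the SAP's .25 is used as a shift in standard deviations.

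- Control, all three: 1/8 + (arcsin .2 + arcsin .2 + arcsin .6)/(4π) = .125 + (.2014 + .2014 + .6435)/12.566 = .208, or 21%.
- Treated, any shifted scale alone: Φ(0 + .25) = .599, a gain of 9.9 points.
- All three scales shift: trivariate normal probability at (.25, .25, .25) = .306, so 21% vs 31%.
- Only drinking shifts: probability at (.25, 0, 0) = .242. The alcohol percentage still rises 9.9 points; the joint rate rises .242 − .208 = 3.4 points.

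**5. Range.** The same formula was run with control rates of 30%, 40%, 50% and 60% and correlations of .1/.5, .2/.6 and .3/.7. The joint control rate runs from 6% to 34% (11% to 34% for control rates of 40–60%). With a drinking-only effect, the alcohol percentage rises 9.2 to 9.9 points and the joint rate 1.5 to 4.0 points. The gap between single-scale and joint gain persists throughout.

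**The case against.** The strongest reply is that the SAP never says each scale separately. It names the same three instruments as the protocol, joined by a conjunction, and may be a loose restatement of the combined outcome. This stands in part: a reader might infer that the SAP has definitely replaced the combined outcome with per-scale percentages, and the text does not go that far. It does not remove the point, because on the charitable reading the outcome still lacks a joining rule, thresholds and a test.

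Nor does the protocol fully define its composite. Because entry is by depression and/or anxiety, alcohol plus either mood scale would also fit the wording. So the statement that different people count as successes holds only under the per-scale reading and an assumed all-three rule. The protocol also speaks of reduction, whereas being below cut-offs is a status that some participants may already meet on one mood scale at baseline. Both observations stand and are reflected in the fix.

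Two further inferences should be resisted:

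- *Multiplicity.* Three scales at two visits, each tested at .05, would give 1 − .95^6 = 26% chance of at least one false positive if independent. The SAP says only "We will also examine overall group differences in clinically meaningful variables" and names no test or alpha, so this describes tests that the plan does not specify.
- *Power.* With 200 per arm, two-sided .05 and all three scales shifting, the step 4 assumptions give power of about .61 for the joint outcome and .51 for a single percentage. At a 30% control rate the order reverses (.43 against .49). With equal correlations from 0 to .7 and control rates of 30–60%, joint power runs from .37 to .74. No power advantage can be claimed.

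Finally, because the AUDIT is scheduled only at baseline, neither version can be computed at T1 or T2 as written. That is correct and must be settled first, but settling it would not by itself create an analysis of the combined outcome.

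**Conclusion.** The point holds in this form: the protocol commits to one combined outcome for clinically significant improvement, and the SAP neither names it, gives a rule for it, nor plans a comparison of it. On its natural reading the SAP offers only single-scale percentages, which cannot show joint improvement in the same participants.

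The logical bounds (0% to 50% joint when each rate is 50%) need no assumption about correlation. The 21% joint rate, and the 3.4-point joint gain against 9.9 points on alcohol alone, rest on assumed control rates, correlations and an all-three rule; none of these is in the documents.

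The change should be made, but the point is not critical: the primary outcome is seven-day drinks on the TLFB, and N does not depend on the combined outcome.

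**What to change.** 1. **Reconcile the alcohol component first.** The baseline-only AUDIT conflicts with its post-treatment use in the protocol's combined outcome and in the SAP. Either add the AUDIT at T1 and T2 or name another alcohol measure collected then. The TLFB is collected at both visits, but the documents give it no clinical threshold, so one would have to be stated and justified.
2. **State one responder definition, worded identically in the protocol (Research Instruments) and the SAP (Statistical Plan).** Count a participant as a responder if below the alcohol cut-off and below both the CES-D and the GAD-7 cut-offs at the same visit. Give the numeric cut-offs and say whether they are the entry cut-offs. The sponsor should confirm the all-three rule, which best fits the stated aim of combined improvement.
3. **Plan the comparison.** Use a logistic GEE comparing arms at T1 and T2, with T1 leading because the power analysis rests on posttreatment. State its place in the testing order and how missing responder status is handled.
4. **Keep the three single-scale percentages** as descriptive components, without separate significance claims.
5. **Report by arm how many participants were already below each mood cut-off at baseline**, since entry allows this.

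The cost is a few sentences in each document, one extra model, and the decision on the alcohol measure, which may add an assessment at T1 and T2. No additional participants are needed. The downside is a headline responder rate that cannot exceed, and will probably be well below, the single-scale rates.

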If individuals meet the eligibility criteria in terms of suicidality (i.e., minimal or low risk), they will then be provided with the remainder of the baseline measures. If participants do not meet our eligibility criteria, we will still provide them with access to the intervention, but will not track their data, and their responses to the baseline measures will not be retained. After eligible participants complete the baseline measures, they will be randomly assigned to one of the two treatment conditions using a 1:1 ratio. The first condition will be the integrated treatment (i.e., active experimental condition) where participants will have access to the 12 treatment modules, developed using combined elements of CBT and MI. Throughout the modules, participants will identify goals related to alcohol use and mood, learn strategies to cope with alcohol cravings, triggers, and social pressures, and learn how to prevent relapse. Modules will also include

content designed to target anxiety and depression, focusing on strategies designed to help reduce negative thinking and worry, increase behavioural activation, and increase self-care (e.g., relaxation techniques, sleep hygiene).

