The second condition will be psychoeducational (i.e., the control condition). Participants randomly assigned to the control condition will receive links to websites that provide general psychoeducation about alcohol (e.g., <https://www.niaaa.nih.gov/publications/brochures-and-fact-sheets>), and mental illness (e.g., <https://www.jack.org/resources>). Therefore, the control group will have access to available online psychoeducational material. A psychoeducation control group is common in clinical research in order to determine the efficacy and effectiveness of online interventions (Schaub et al., 2016). It is also important as we do not want to harm patients in any way or prevent them from getting something that is already established are effective. For ethical reasons, participants in the psychoeducation control group will be given access to the active integrated treatment at the end of the study, regardless of whether they have completed all of the assessments.

*Research Instruments:* Participants will be assessed at three time points throughout the study: at baseline (i.e., prior to treatment; T0), immediately following the 8-week treatment (T1), and at follow-up (i.e., 24 weeks, T2). The primary outcome of interest will be the number of standard drinks consumed during the seven days prior to the assessment. This will be assessed using the Timeline Follow-Back (TLFB; Sobell & Sobell, 1992) procedure at all assessment points (T0-T2). The TLFB has been widely used in studies, including treatment studies (Keough, O'Connor, & Colder, 2016; Schaub et al., 2016). As a secondary outcome, depressive symptoms will also be assessed at all time points using the CES-D, a 20-item self-report questionnaire used to indicate

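### The pre/post GEE does not specify how baseline enters or which contrast and time point decide; its most natural reading is valid but never more efficient than a baseline-adjusted T1 contrast

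*SAP*

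**What the plan says.** The SAP's Power Analysis paragraph sizes the trial on a between-arm difference at a single time point: g = .25 "is expected for group differences in alcohol use and emotional symptoms at posttreatment", giving N = 398 at power .80 and alpha .05.

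The Statistical Plan paragraph then turns to change. GEE "will be used to evaluate the main hypotheses that integrated treatment will result in the largest reductions in alcohol use, depression, and anxiety". The method is justified by the statement that "GEE is a multilevel modeling technique that is preferable to repeated-measures ANOVA for pre/post analyses". The reason offered is that nobody who was randomized has to be left out of the model. The design of the test is given as: "Primary and secondary outcomes will be tested sequentially in a mixed within- (repeated assessments) and between-subjects (treatment condition) design".

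The paragraph states no mean model, link, working correlation, tested coefficient or deciding time point. Baseline is otherwise mentioned only as a preliminary check for differences between arms.

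The Protocol's Method section measures past-week drinks, the primary outcome, at T0, T1 (after the 8-week treatment) and T2 (24 weeks), and does not choose between T1 and T2. It also fixes the order of events: "After eligible participants complete the baseline measures, they will be randomly assigned to one of the two treatment conditions using a 1:1 ratio". T0 is therefore a true pre-randomization measurement, available for every randomized participant.

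**The concern.** Several different tests fit the wording, and they differ in power. An analyst could fit arm, visit and their interaction with a free baseline mean in each arm, and test the T0-to-T1 change. Another could fit a common baseline mean and test the arm difference at T1. Either could use T2, or a joint test over both follow-ups.

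References to pre/post analysis, to reductions, and to repeated assessments crossed with condition point most naturally to the first of these. That contrast subtracts the whole baseline value, although randomization already makes the expected baseline means equal. It therefore carries noise that a baseline-adjusted contrast removes.

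At stake are precision that can be had without cost and a deciding test that is fixed before the data are seen. The target of 400 exceeds the stated requirement by two, and the SAP itself anticipates attrition.

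**Working it through.** **Inputs.** From the documents: g = .25, power .80, alpha .05, N = 398 (SAP, Power Analysis); target 400 (Protocol, Participants); 1:1 allocation (Protocol, Method), hence 200 per arm. Not in the documents and therefore assumed: the T0-T1 correlation r = .3, .5, .7; the ratio q = SD(T0)/SD(T1); the proportion observed at T1.

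**1. The plan's own figure.** For a two-sample t-test at d = .25, the smallest N reaching 80% power is 398 one-sided (power .801) and 506 two-sided. The stated 398 thus matches an unadjusted, one-sided comparison at one time point. Sidedness is a separate matter; one-sided power comes first below only because it reproduces the plan's number.

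**2. Relative variance of the T1 effect** (posttreatment comparison = 1; identity link, equal variances, complete data):
- change contrast: 2(1 − r)
- baseline-adjusted contrast: 1 − r²
- information lost by change against adjusted: 1 − (1 − r²)/[2(1 − r)] = (1 − r)/2
- change against posttreatment: 1/[2(1 − r)] − 1

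| | r = .3 | r = .5 | r = .7 |
|---|---|---|---|
| Variance, change | 1.40 | 1.00 | .60 |
| Variance, adjusted | .91 | .75 | .51 |
| Loss, change vs adjusted | 35% | 25% | 15% |
| 400 participants are worth | 260 | 300 | 340 |
| Change vs posttreatment | −29% | 0 | +67% |
| One-sided power, change / adjusted | .68 / .83 | .80 / .89 | .94 / .97 |
| Two-sided power, change / adjusted | .56 / .74 | .70 / .82 | .90 / .94 |

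**3. Unequal variances.** In units of the T1 variance, the change contrast has variance q² + 1 − 2rq and the adjusted contrast 1 − r². The difference is (q − r)², which is never negative, so the ordering does not depend on the assumptions. The loss is (q − r)²/(q² + 1 − 2rq):
- q = .8: .25/1.16, .09/.84, .01/.52 = 22%, 11%, 2%
- q = 1.2: .81/1.72, .49/1.24, .25/.76 = 47%, 40%, 33%

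**4. Attrition.** Suppose 140 of 200 per arm are observed at T1, missing at random, with all T0 values kept (equal variances). Per-arm variance is (1 − r²)/140 + (1 − r)²/200 for change and (1 − r²)/140 for adjusted:
- r = .3: .00895 vs .00650, loss 27%
- r = .5: .00661 vs .00536, loss 19%
- r = .7: .00409 vs .00364, loss 11%

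One-sided power is .59/.70/.87 against .71/.78/.90.

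**5. Working correlation.** This is the robust (sandwich) variance of the T1 arm effect in a three-visit GEE with a common T0 mean, when the true correlation is exchangeable, relative to the posttreatment comparison:
- exchangeable working correlation: .91, .75, .51
- independence working correlation: 1.00, 1.00, 1.00

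Under independence, T0 contributes nothing to the T1 arm estimate, which becomes the raw posttreatment difference. At r = .7 it has 1 − .60/1.00 = 40% less information than the change contrast.

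**6. Drink count.** One simulation used a negative binomial outcome (assumed mean 20, SD 17), three visits, a log link, an unstructured working covariance, 200 per arm and 2,000 replicates. At achieved r of .29, .47 and .68, one-sided power was .76, .87 and .97 with free T0 means and .91, .94 and .99 with a common T0 mean. This supports the ordering, not the percentages in step 2.

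**The case against.** **It is an efficiency preference, not an error.** This stands. The change contrast is unbiased and holds its type I error rate in a randomized trial. On the plan's apparent one-sided basis with complete data, it reaches .80 at r = .5 and .94 at r = .7. A reader might infer that the trial is underpowered against its own sizing. With equal variances that follows only if r < .5, and the documents give no r.

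**T0 does have a role.** Also right. A reader might infer that the plan discards baseline, but the pre/post wording makes T0 one of the repeated outcomes. What is missing is how it enters the model. Likewise, the SAP does name a time point, but only for sizing.

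**The percentages rest on one reading and on unstated quantities.** This stands too. The range of 2% to 47% shows how far they move. Eligibility screening on CES-D and/or GAD-7 could narrow the T0 spread on those secondary outcomes. With the T1-on-T0 slope and residual variance held fixed and T0 SD assumed at .8 of its unscreened value, the loss is .64(1 − r)²/[1 − r² + .64(1 − r)²] = 26%, 18%, 10%.

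**The wording also fits a common-T0-mean model.** True, but that model avoids the loss only under a non-independence working correlation, and the SAP states none. This does not remove the point. It shows that power depends on choices the plan leaves open.

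**Conclusion.** The point holds as a free improvement together with a test that needs pinning down. The SAP does not specify how T0 enters the GEE, which contrast decides, or at which time point. Its most natural reading is valid but never more efficient than a baseline-adjusted T1 contrast. That ordering holds at every r and every T0/T1 variance ratio on the continuous scale.

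The size is illustrative: 35%, 25% or 15% at assumed r of .3, .5 or .7 with equal variances and complete data; about 2% to 47% over SD ratios of .8 to 1.2; and 27%, 19% or 11% if 70% are observed at T1. These levels should not be read as the established loss for the primary outcome. For a drink count with a log link, only the ordering is supported. Nor do the documents support a claim of bias or of an inflated false-positive rate.

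**What to change.** Prespecify in the SAP:

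- A GEE with T0, T1 and T2 as outcomes, visit terms, and arm terms at T1 and T2 only, so that the arms share one T0 mean. Baseline precedes randomization, so this constraint holds by design. All randomized participants stay in the model, as the SAP intends.
- A non-independence working correlation (unstructured, or exchangeable) with robust standard errors. Independence should be ruled out explicitly: T0 would then add nothing to the T1 arm estimate, and with equal variances the test would be weaker than the change contrast whenever r > .5.
- The link for the 7-day drink count.
- The T1 arm contrast on 7-day drinks as the primary test, since T1 is the time point the SAP powers.
- The same model for CES-D and GAD-7.

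A GEE on T1 and T2 with the T0 value as covariate is an alternative. Its drawback is that participants missing both follow-ups contribute no outcome rows. If it is chosen, the SAP should disclose this, because it departs from the stated aim of including everyone randomized.

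The cost is SAP wording only: no added participants, visits or measurements.
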